#### 16.2.2 Stopping Rule

The PIs will monitor the blood transfusion ordered and the units transfused before patients' discharge. In any case, blood transfusion with more than 2 units (BT2U) happens, the trial will pause to examine the cause and decide whether to continue or terminate the trial due to the safety concern. The trial will be terminated if the accumulative relevant BT2U number reaches to six for nephrectomy (24%) or two for thoracotomy (8%). The stopping rule is to stop the trial early due to any high chance of toxicity.

#### 16.2.3 Analysis of safety data

All subjects who receive Ketorolac will be included in the summaries and listings of safety data. Overall safety profile will be characterized by type, frequency, severity, timing, during, and relationship of Ketorolac. The rate of pre-discharge blood transfusion and the mean blood unit transfused will be summarize by frequency and proportion with 95% confidence interval for the rate of AEs, and mean (range) and 95% Wald confidence interval.

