## 1. Study Summary

Study Title	A Pilot Study of Biomarker Evaluation and Safety of Pre-Incisional Ketorolac for Patients Undergoing Surgical Resection for Non-Small Cell Lung Cancer and Renal Cell Carcinoma
Study Design	
PATIENT REGISTRATION/RANDOMIZATION
 
Patients will be screened and recruited during the pre-operative period by the responsible medical and surgical team. Blood will be drawn pre-operatively and then at the end of the surgical procedure. Patients who are eligible to be included will be fully informed, consented for additional blood draws and will have the opportunity to ask any questions they may have.
 
Patients will be randomized to either pre-operative Ketorolac group or a concurrent control group who will not receive pre-incisional ketorolac. The concurrent control group is to obtain untreated biologic samples for biologic correlative studies and secondary endpoints. These patients will not be compared to the investigational cohort in regards to the primary endpoint of safety. Patients will be randomized on the day of surgery to either the experimental or control arms. A total of 56 patients will be enrolled into the experimental arm (28 per disease site). About 10 patients will be allocated randomly into the concurrent control group for each disease site separately, for a total of 76 patients enrolled. The enrolment for NSCLC will cease at total of 28 patients consented with total study enrolment goal of 79 Up to 80 patients may be consented on study to account for screen fails and/or withdrawals.

Primary Objective	To test the safety of a single pre-incisional dose of 30 mg ketorolac in patients undergoing surgery for stage I/II NSCLC and stage III RCC, as these are the stages of cancer most likely to develop a recurrence while still noting a benefit from the ketorolac.
Secondary Objective(s)	To evaluate blood and tissue samples pre- and post-operatively to assess the impact of ketorolac on key

	inflammatory biomarkers using a standard cytokine panel.

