#### 4. Study Endpoints

##### 4.1 Primary Safety Endpoints

Incidence of clinically significant pre-discharge (both intra- and post-operative) blood transfusion, clinically significant hematoma development, or return to the operating room for bleeding; post-operative renal failure; and post-operative morbidity rates.

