## 16.2 Statistical Consideration

### 16.2.1 Sample size determination

It is a pilot study that aims to monitor the hemorrhage side effects who received Ketorolac pre-operatively with the primary safety endpoint being pre-discharge blood transfusion. According to the historical data, among 3280 nephrectomy cases during 2015-2020 in Emory, 20% need a blood transfusion before the discharge, and the mean number of units transfused is 0.286 (standard deviation = 0.12). Among 1212 thoracotomy cases during 2014 -2020 in Emory, 3.4% need a blood transfusion before the discharge, and the mean number of units transfused is 0.098 (standard deviation = 0.075). We anticipate a similar safety profile among the patients who received the pre-operative Ketorolac in this study. A sample size of 50 (25 patients in each disease site) produces a one-sided 90% confidence interval with an upper limit of 0.12 (the distance from the mean number of units transfused to the upper limit = 0.02) for thoracotomy. For nephrectomy, the upper limit of a one-sided 90% confidence interval would be 0.318 (the distance from the mean number of units transfused to the upper limit = 0.032). To account for a possible 10% drop off, we will plan to enroll 28 patients in each disease type.

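### The 95% Wald interval planned for mean units transfused collapses to [0, 0] if no lung ketorolac patient is transfused, a 38 to 42% chance at the plan's own 3.4% rate (by-site summary assumed)

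*Combined protocol and SAP*

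**What the plan says.** Section 16.2.3 defines the analysis set: "All subjects who receive Ketorolac will be included in the summaries and listings of safety data". It then asks for the pre-discharge transfusion rate with a 95% confidence interval, naming no method, and for mean units transfused as "mean (range) and 95% Wald confidence interval". It does not say whether these summaries are by disease site or pooled, or what to do if no one is transfused.

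The other relevant places are:

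- **Section 16.2.1** gives the lung history: "Among 1212 thoracotomy cases during 2014 -2020 in Emory, 3.4% need a blood transfusion before the discharge". It expects a similar profile on ketorolac. It bases the sample size on mean units in each site, with 25 evaluable and 28 enrolled patients per site; for thoracotomy it gives "the distance from the mean number of units transfused to the upper limit = 0.02".
- **Section 16.2.2** sets separate stopping counts for nephrectomy (six) and thoracotomy (two).
- **Section 4.1** words the primary safety endpoint as an incidence: "Incidence of clinically significant pre-discharge" transfusion and other bleeding events, among other outcomes.
- **Section 1** now limits lung accrual: "The enrolment for NSCLC will cease at total of 28 patients consented". It gives no split of those 28 by arm.

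**The concern.** A Wald interval for a mean is the mean plus or minus 1.96 × SD/√n. It relies on the sample SD being a fair estimate of spread. When the event is rare and the sample small, the most likely departure is a sample with no events at all. Every value is then 0, the SD is 0, and the interval has no width.

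In the lung group fewer than one transfused patient is expected, so this is one of the most likely results. The table would then show mean units of 0 with a 95% interval of [0, 0], which claims certainty that 25 to 28 patients cannot give. The error is also in the unsafe direction, because it understates possible bleeding in a study meant to establish safety before a larger trial.

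**Working it through.** **1. The plan's own figures reproduce.** Upper limit = mean + t(0.90, 24 df) × SD/√25, with t = 1.318.

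- Thoracotomy: 1.318 × 0.075/5 = 0.0198; 0.098 + 0.0198 = 0.118, stated as 0.12.
- Nephrectomy: 1.318 × 0.12/5 = 0.0316; 0.286 + 0.0316 = 0.318, as stated.
- Enrolment: 25/0.90 = 27.8, rounded up to 28.

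**2. Chance that no lung ketorolac patient is transfused.** With p = 0.034 from section 16.2.1, the expected number transfused is 25 × 0.034 = 0.85 or 28 × 0.034 = 0.95. P(none) = (1 − p)^n.

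| Lung ketorolac n | P(none) at 3.4% | P(none) at 6.8% (rate doubled) |
|---|---|---|
| 25 | 0.966^25 = 0.421 | 0.932^25 = 0.172 |
| 28 | 0.966^28 = 0.380 | 0.932^28 = 0.139 |

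If the cap of 28 lung consents covers both arms in the planned 28:10 ratio (an assumption), about 28 × 28/38 = 20.6 patients receive ketorolac. P(none) at 3.4% is then 0.966^21 = 0.484 or 0.966^20 = 0.501.

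**3. What the planned interval prints in that case.** Mean = 0, SD = 0, half-width = 1.96 × 0/√n = 0, so the interval is [0, 0]. Any other multiplier also gives 0, so using t in place of 1.96 does not help.

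**4. Coverage of the nominal 95% Wald interval for lung mean units.** The plan implies 0.098/0.034 = 2.88 units per transfused patient. Assume each transfused patient receives 2 units (12%) or 3 units (88%), which has that mean. Exact enumeration gives:

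| n | Coverage | Upper limit below true mean | Lower limit above true mean |
|---|---|---|---|
| 25 | 0.578 | 0.4211 | 0.0012 |
| 28 | 0.619 | 0.3796 | 0.0014 |

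At n = 20 coverage is 0.499. Misses that understate the mean are 0.4211/0.4223 = 99.7% of all misses at n = 25, and 0.3796/0.3810 = 99.6% at n = 28. Across four assumed spreads of units with the same mean, coverage stays at 0.578 to 0.579 (n = 25) and 0.619 to 0.622 (n = 28).

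The reason is simple: coverage is almost exactly 1 − P(none). A single transfused patient is usually enough for the interval to cover. For example, one patient of 25 with 3 units gives mean 0.12, SD 0.6, and interval 0.12 ± 1.96 × 0.6/5 = −0.115 to 0.355, which contains 0.098.

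**5. The transfusion rate, for comparison.** The exact (Clopper-Pearson) upper limit at zero events is 1 − 0.025^(1/n): 13.7% for 0/25 and 12.3% for 0/28. Its actual coverage at 3.4% is 0.990 (n = 25) and 0.986 (n = 28). If a Wald interval were chosen for the rate as well, coverage would be 0.577 and 0.618.

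**The case against.** The strongest objection is that section 16.2.3 never says the summary is by site. Pooled over both sites, at the plan's 20% nephrectomy rate, the chance of no transfusion is 0.966^25 × 0.8^25 = 0.16% (0.07% with 28 per site), and the problem all but disappears. The text leaves that reading open. But sections 16.2.1 and 16.2.2 both work by site, and only a by-site mean can be set against the separate precision targets of 0.12 and 0.318. Pooling a 20% and a 3.4% population could also hide a lung signal. The nephrectomy group alone is hardly affected: 0.8^25 = 0.4%.

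Other points that carry weight:

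- **The harm is limited.** No stopping decision uses this interval. The rate and the range are reported alongside, so a careful reader would see 0/n. This is a descriptive pilot.
- **The coverage figures are not a second fault.** They restate P(none), as step 4 of the working shows.
- **Sizing used a different interval.** Section 16.2.1 uses a one-sided 90% limit. The measure is the same, however, and that limit would also collapse at zero events.
- **The rate point is conditional.** Section 16.2.3 attaches Wald to the mean only, and an exact method for the rate is compatible with its text.
- **The SD in section 16.2.1 is a problem of its own.** A 3.4% rate with mean 0.098 needs an SD of at least √(0.034 × 2.88² − 0.098²) = 0.52, against the stated 0.075. This does not affect the zero-event probability, which depends only on the rate and n.
- **The lung cohort is closed and may be smaller than planned.** A smaller cohort raises the risk. Lung ketorolac recipients remain in the safety summaries, and analysis text can still be changed.

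**Conclusion.** The concern holds. Following section 16.2.3 as written would print a 95% interval of [0, 0] for lung mean units with probability 38% (n = 28) to 42% (n = 25), or 48 to 50% if the lung cap covers both arms in the planned ratio. If ketorolac doubled the lung rate, it would still appear with probability 14 to 17%.

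This rests on two assumptions: that results are summarised by site, and that the lung rate on ketorolac is the historical 3.4% that the plan itself expects. The result barely depends on how units are distributed among transfused patients. The method should be changed, but the defect does not put the conduct of the trial or its stopping decisions at risk.

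**What to change.** In section 16.2.3, state that the proportion transfused is reported by disease site with an exact (Clopper-Pearson) 95% interval, as the main summary of the transfusion endpoint. This fits the incidence wording of section 4.1 and settles the unnamed method for the rate. Report total, mean and range of units descriptively without a Wald interval, or with a method that does not rely on the sample SD when events are zero or very few.

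The cost is one sentence of analysis text, with no change to sample size or data collection. Exact intervals are wider and conservative, with about 99% actual coverage at a 3.4% rate.

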#### 16.2.4 Analysis of the secondary endpoints

For all biomarkers, descriptive statistics (means, medians, standard deviations, interquartile range) and graphical displays will be used to characterize central tendency and variability over time. Values will be log transformed as appropriate to reflect biologic plausibility.

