### 2.2 Secondary Objective

To evaluate blood and tissue samples pre- and post-operatively to assess the impact of ketorolac on key inflammatory biomarkers using a standard cytokine panel.

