##### 4.2 Secondary Endpoints

A number of exploratory biological correlative studies including transcriptome analysis, flow cytometry, TCR sequencing and single cell RNA Seq to evaluate the effects of ketorolac on immune response pathways.

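### The biomarker analysis in Section 16.2.4 states no between-arm contrast, baseline adjustment or interval, although the secondary objective is the effect of ketorolac and controls are randomised for it

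*Combined protocol and SAP*

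**What the plan says.** The secondary objective (Section 2.2) is to "assess the impact of ketorolac on key inflammatory biomarkers using a standard cytokine panel". Section 4.2 lists exploratory correlative studies "to evaluate the effects of ketorolac on immune response pathways". Both describe a treatment effect.

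The Study Summary (Section 1) randomises patients on the day of surgery and gives the control arm's purpose: "The concurrent control group is to obtain untreated biologic samples for biologic correlative studies and secondary endpoints". It adds: "These patients will not be compared to the investigational cohort in regards to the primary endpoint of safety". On size it says: "About 10 patients will be allocated randomly into the concurrent control group for each disease site separately", against 28 per site on ketorolac. It also says: "The enrolment for NSCLC will cease at total of 28 patients consented", with a total enrolment goal of 79.

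The only analysis text for these endpoints is Section 16.2.4: "descriptive statistics (means, medians, standard deviations, interquartile range) and graphical displays will be used to characterize central tendency and variability over time", with log transformation where appropriate. The intervals in Section 16.2.3 and the equality test in Section 16.3 concern safety.

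Section 7.1 also sets an aim for tissue: to describe how lymphatic and blood vessels differ before and after treatment.

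**The concern.** The objective asks what ketorolac does, and the analysis text describes how values move over time. Section 3 itself says that surgery provokes inflammation and immunosuppression. A post-operative change in CRP, IL-6 or NLR in treated patients therefore reflects the operation as well as the drug, and the randomised controls are what separates the two. Section 16.2.4 does not say how they will be used.

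With few controls, arm means shown without an interval are easy to over-read. Section 3 places this pilot ahead of a larger phase II study, so an apparent biomarker signal, or its absence, may influence that study.

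**Working it through.** **1. The plan's own figures.** No sample size or precision is given for biomarkers. The only precision figures are for units transfused (Section 16.2.1), as mean + t(0.90, 24) × SD/√25 with t = 1.318:
- nephrectomy: 0.286 + 1.318 × 0.12/5 = 0.286 + 0.032 = 0.318, as stated;
- thoracotomy: 0.098 + 1.318 × 0.075/5 = 0.098 + 0.020 = 0.118, stated as 0.12.

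They reproduce, but say nothing about biomarkers.

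**2. Precision of an arm difference.** No biomarker variance is given, so results are in SD units (log scale where used). Half-width of the 95% CI = t(0.975, n1+n2−2) × √(1/n1 + 1/n2).
- RCC as planned, 28 vs 10: 2.028 × 0.368 = 0.75.
- RCC if the goal of 79 is read as 79 − 28 = 51 RCC patients, split 38 vs 13 (assumed, close to 28:10): 2.010 × 0.321 = 0.65. The Study Summary does not say whether the 79 includes screen failures.
- NSCLC, 28 consented with no arm split stated. Assumed 18 vs 10: 2.056 × 0.394 = 0.81. Assumed 21 vs 7 (about 28:10): 2.056 × 0.436 = 0.90.
- Pooled, stratified by site, with weight n1·n2/(n1+n2) per site and N−3 degrees of freedom:
  - 28 vs 10 plus 21 vs 7: weights 7.37 + 5.25 = 12.62; 1.998/√12.62 = 0.56.
  - 38 vs 13 plus 18 vs 10: weights 9.69 + 6.43 = 16.11; 1.992/√16.11 = 0.50.

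**3. Gain from baseline adjustment.** The half-width is multiplied by about √(1 − ρ²). With an assumed pre/post correlation of 0.5 the factor is 0.87; with 0.7 it is 0.71. For RCC at 28 vs 10, 0.75 becomes about 0.65 to 0.53.

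**4. Chance differences.** With no drug effect, the standard error at 28 vs 10 is 0.368 SD. The chance that the arm means differ by more than 0.5 SD is 2 × P(Z > 0.5/0.368) = 2 × P(Z > 1.36), about 17%.

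**5. Which draw can be the baseline.** The documents place the day-of-surgery draw differently:
- Study Summary: "Blood will be drawn pre-operatively and then at the end of the surgical procedure";
- Section 6.1: day 0, with no time given;
- Section 7.2 text: the preoperative holding area;
- Section 7.2 table: a day-of-surgery sample listed as pre-surgery.

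An end-of-procedure sample follows the induction dose. It can be an outcome, but adjusting for it could remove part of the effect being estimated.

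**6. Tissue.** The calendar has one tissue collection, on day 0. Section 7.1 takes it at surgery, if enough remains after clinical needs, and Section 5.2 gives ketorolac at induction. The scheduled tissue is therefore all post-dose, and the plan has no pre-treatment sample to set against it.

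**The case against.** The strongest reply is that description suits this study. It is a pilot, Section 4.2 calls the correlative studies exploratory, and the sample size rests on transfusion alone. Controls were randomised for these endpoints, so tables by arm are the natural reading of Section 16.2.4. From by-arm means, SDs and counts, any reader can compute a crude difference and an unadjusted interval. The control profile would also show the effect of surgery.

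Much of this stands. A reader might infer that the plan makes the effect of ketorolac impossible to estimate, or that it forbids comparing the arms on biomarkers. The documents support neither: the Study Summary excludes the controls only from the primary safety comparison. Nor do they call for a powered test of an exploratory endpoint.

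Two further objections limit the remedy. An interval of 0.50 to 0.90 SD either way will seldom settle whether a change is due to the drug. And intervals multiply: three markers at three post-operative visits, pooled and for each of two sites, make 3 × 3 × 3 = 27, of which 27 × 0.05 = 1.35 would be expected to exclude no effect by chance. The contrast should therefore be confined to a short named list.

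The reply does not supply a stated contrast, a baseline-adjusted estimate or its precision. By-arm summary tables do not carry the within-patient correlation that adjustment needs. Nor does it rescue the before/after tissue aim.

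**Conclusion.** The point holds as a gap in specification. The secondary objective is a drug effect and the controls exist to show it, but Section 16.2.4 states no arm contrast, baseline adjustment or interval. The primary safety objective is unaffected.

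Expected unadjusted half-widths are about 0.75 SD for RCC (0.65 if 38 vs 13), 0.81 to 0.90 SD for NSCLC, and 0.50 to 0.56 SD pooled. Baseline adjustment would multiply these by about 0.87 to 0.71. The NSCLC split, the 38 vs 13 split and the correlations are assumptions. The counts also take every patient as contributing a sample, so missing draws, or benign pathology (not counted under Section 6.3), would widen the intervals.

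The 56 vs 20 in the planned totals should not be used for the pooled precision: 28 ketorolac plus 10 control patients with NSCLC cannot fit within 28 consented.

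**What to change.** In Section 16.2.4:
- Summarise every biomarker by arm and disease site, with numbers at each visit.
- For a short named list of blood markers (for example NLR, CRP and IL-6) at one named post-operative visit, report the ketorolac-to-control ratio or difference with a 95% CI, adjusted for a pre-dose value and disease site.
- Present other markers, other visits and by-site estimates as supportive.
- Label all of it exploratory and not adjusted for multiplicity, and post hoc if data have already been examined. Section 9 closes enrolment, so that label may well be needed.
- Name a clearly pre-dose draw as baseline, and reconcile the day-of-surgery draw across the Study Summary, Section 6.1 and Section 7.2.

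In Section 7.1, replace the before/after tissue aim with a day-0 comparison between arms, adjusted for site. Report how many patients per arm had adequate tissue, since they may be a selected group.

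The cost is a little more analysis, with no new patients or samples. The intervals will be wide and will seldom settle the question, but they show the uncertainty before a larger study is planned.

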### 16.3 EVALUATION OF OUTCOMES

All patients will be followed for adverse events including surgical morbidity and mortality for 90 days after surgery. Toxicity will be graded according to the NCI CTC version 4.4. The rates of all Grade 3-5 adverse events during or within 90 days of surgery will be tested for equality using a two-sided chi-square test or Fisher's exact test with a 0.05 significance level.

#### 16.3.1 Overall safety assessment

The primary objective is to assess the safety data by using ketorolac pre-operatively, and we plan to longitudinally collect safety data from each patient. The study team will meet on a regular basis to review safety events and make decision about trial stopping based on the safety concerns.

#### 16.3.2 Bleeding

Post-operative bleeding will be assessed as follows:

16.3.2.1 Need for return to the operating room for bleeding as determined by the treating surgeon

16.3.2.2 Need for transfusion, > 2units of blood, which are not related to vascular injury due to technical considerations or complications, as determined by the operating surgeon.

16.3.2.3 Hemoglobin < 7.0 postoperatively, regardless of whether transfusion has occurred.

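### The count of transfusions above 2 units depends on the operating surgeon's view of cause, with no criteria or blinding described, so it can only be lowered; report the all-cause count beside it

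*Combined protocol and SAP*

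**What the plan says.** Section 16.3.2 lists three ways in which post-operative bleeding is assessed.

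- Reoperation: "Need for return to the operating room for bleeding as determined by the treating surgeon". No cause is excluded.
- Transfusion of more than 2 units, limited to cases "which are not related to vascular injury due to technical considerations or complications, as determined by the operating surgeon".
- Low hemoglobin: "Hemoglobin < 7.0 postoperatively, regardless of whether transfusion has occurred". No cause is excluded.

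Section 16.2.2 pauses the trial at any transfusion above 2 units (BT2U), whatever its cause. It terminates the trial "if the accumulative relevant BT2U number reaches to six for nephrectomy (24%) or two for thoracotomy (8"%). The word *relevant* is not defined.

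The sizing in Section 16.2.1 uses a different quantity, any transfusion before discharge. For nephrectomy: "among 3280 nephrectomy cases during 2015-2020 in Emory, 20% need a blood transfusion before the discharge". The stated average there is 0.286 units (SD 0.12). For thoracotomy: "Among 1212 thoracotomy cases during 2014 -2020 in Emory, 3.4% need a blood transfusion before the discharge", with a mean of 0.098 units. No cause filter and no unit threshold are stated for these figures. Section 16.2.3 summarises the same two quantities, the transfusion rate and the mean units, in everyone who receives ketorolac, again with no filter.

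Section 4.1 speaks of clinically significant transfusion without defining it. Section 1 says the concurrent controls are not compared with the ketorolac group on the primary safety endpoint.

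**The concern.** The surgeon who performed the operation decides whether a large transfusion counts against the drug. The plan gives no definition of a technical cause, describes no blinding and no second assessor, and does not ask for a record of what was excluded. A rule that only removes events can move the count in one direction only.

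The excluded events are not clearly unrelated to ketorolac. Section 3 gives platelet inhibition as the reason for concern about bleeding. A drug that impairs platelet function could enlarge a bleed that began as a small vascular injury, so a technical origin does not rule out a drug contribution. These are also the largest transfusions in the trial.

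Two uses of the count are at stake: the above-2-unit bleeding result as reported and, if *relevant* carries the same meaning, the tally that ends the trial.

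**Working it through.** **Inputs.** Boundaries of 6 and 2 (Section 16.2.2); 25 patients per disease site, transfusion rates of 20% and 3.4%, mean units of 0.286 and 0.098, SDs of 0.12 and 0.075 (Section 16.2.1). The documents give neither the share of above-2-unit events excluded (e) nor the true above-2-unit rate (p) under ketorolac. Both are assumptions below.

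**1. The plan's own figures.** 6/25 = 24% and 2/25 = 8%, as stated. The one-sided 90% upper limits are mean + t(0.90, 24 df) × SD/√25, with t = 1.318:

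- nephrectomy: 0.286 + 1.318 × 0.12/5 = 0.286 + 0.0316 = 0.318 (plan: 0.318)
- thoracotomy: 0.098 + 1.318 × 0.075/5 = 0.098 + 0.0198 = 0.118 (plan: 0.12)

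These limits concern mean units over all patients. The surgeon's exclusion does not enter them.

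**2. Where the filter applies.**

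| Quantity | Section | Surgeon filter? |
|---|---|---|
| Any-transfusion rate, mean units | 16.2.3 | No |
| Pause at any BT2U | 16.2.2 | No |
| Return to operating room | 16.3.2.1 | No |
| Transfusion above 2 units | 16.3.2.2 | Yes |
| Hemoglobin below 7.0 | 16.3.2.3 | No |
| Termination tally | 16.2.2 | Unclear: *relevant* is undefined |

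**3. Effect on the termination tally, if *relevant* means the same filter.** The counted rate is p(1 − e). The chance of reaching boundary r within 25 patients is P(X ≥ r) for X ~ Binomial(25, p(1 − e)).

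| e (assumed) | Nephrectomy, p = 30%, r = 6: counted rate | P(X ≥ 6) | Thoracotomy, p = 8%, r = 2: counted rate | P(X ≥ 2) |
|---|---|---|---|---|
| 0 | 30% | 0.81 | 8% | 0.61 |
| 20% | 24% | 0.58 | 6.4% | 0.48 |
| one third | 20% | 0.38 | 5.3% | 0.39 |
| 50% | 15% | 0.16 | 4% | 0.26 |

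One excluded patient changes the above-2-unit rate by 1/25 = 4 percentage points. With a thoracotomy boundary of two, reclassifying one of two events halves the tally.

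**4. How common such transfusions were historically.** Assume whole units. Each transfused patient then has at least 1 unit, and a patient above 2 units has at least 3, that is, 2 or more beyond the first. So the historical above-2-unit rate is at most (mean units − transfusion rate)/2:

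- nephrectomy: (0.286 − 0.20)/2 = 0.043, or 4.3%
- thoracotomy: (0.098 − 0.034)/2 = 0.032, or 3.2%

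The assumed 30% and 8% in step 3 are therefore well above anything the historical figures allow. They describe what the filter does when large bleeds have become much more frequent. At 4.3%, the chance of 6 or more in 25 nephrectomy patients is about 0.001 even with no filter, so there the exclusion hardly matters to the rule.

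**The case against.** The strongest reply is that the quantities matching the historical figures carry no filter. Section 16.2.1 names pre-discharge transfusion as the primary safety endpoint, and Section 16.2.3 reports its rate and the mean units for all ketorolac recipients. Nothing in the plan compares the Section 16.3.2.2 count with 20% or 3.4%, and no formal test against history is specified. This stands.

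A reader might infer from the surgeon's exclusion that the trial as a whole is biased toward looking safe against its benchmark, or that excluding one event in three would turn a 20% rate into 20% × (1 − 1/3) = 13%. The documents do not support either. The 20% is a rate of any transfusion, while the exclusion acts only above 2 units. On the historical figures, removing every above-2-unit nephrectomy patient would take 20% down to 20 − 4.3 = 15.7% at the lowest, and Section 16.2.3 removes none. If someone did set the above-2-unit count beside 20% or 3.4%, the unit threshold would make the two non-comparable even without the surgeon's judgement.

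It can also be said that the pause applies to every BT2U, that the investigators monitor all units given, that two of the three bleeding criteria are unfiltered, and that Section 16.3 covers all Grade 3-5 adverse events. All true. These soften the problem, but none of them commits the trial to reporting an unfiltered count of large transfusions.

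Finally, Section 9 says that the study is to be closed to enrollment. The stopping-rule effect is then largely retrospective. That also stands, and it moves the weight of the point to reporting.

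**Conclusion.** The point holds for the above-2-unit bleeding count. As defined, that count can only be lowered by an unblinded judgement without stated criteria, and the events removed are not clearly independent of the drug. It holds for the termination tally only if *relevant* in Section 16.2.2 means the exclusion in Section 16.3.2.2. That is a plausible reading, but the text does not confirm it.

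The size cannot be derived from the documents. The falls in step 3 (0.81 to 0.58-0.16 for nephrectomy, 0.61 to 0.48-0.26 for thoracotomy) rest on assumed true rates of 30% and 8% and an assumed excluded share of 20% to 50%. They also assume independent patients and 25 per site.

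It does not follow that the primary safety summary is biased: the Section 16.2.3 rate and mean are unfiltered. One loose end is Section 4.1. If its clinically significant transfusion were defined through Section 16.3.2.2, the filter would reach a primary endpoint, and the plan does not say whether it is.

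**What to change.** 1. Keep the any-transfusion rate and mean units in Section 16.2.3 as the primary summary. They are the quantities that match the historical figures.
2. In Section 16.3.2.2, make the main above-2-unit count all patients transfused more than 2 units before discharge, whatever the attribution. Show the count the surgeon judged non-technical as secondary, and list the reason for each exclusion.
3. State that neither above-2-unit count is to be compared with the 20% or 3.4% any-transfusion rates.
4. Reconcile *relevant* in Section 16.2.2 with Section 16.3.2.2, and say which meaning was applied during the trial.
5. Reconcile clinically significant transfusion in Section 4.1 with Sections 16.2.1, 16.2.3 and 16.3.2.

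The cost is analysis-plan wording and one extra table row. Units transfused are already monitored under Section 16.2.2, so no new data and no adjudication committee are needed. The drawback is that the main above-2-unit count will include some bleeds that have nothing to do with ketorolac. The secondary row and the listed reasons let a reader see how many the surgeon judged to be of that kind.
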